APPENDIX 2. TIPPING POINT ANALYSIS

Let delta (shift) be the penalty to TEV-50717 group, ie. the worsening of effect for the patients in TEV-50717 group who early dropped out, compared to patients with full data, assuming MNAR. Delta will be in the range of 0 to 2 (or estimated treatment effect from primary analysis if it is larger than 2) in step of 0.2. The following 3 steps will be performed to do the multiple imputation analysis:

1. Create complete data sets using imputation for each shift in treatment effect.
2. Analyze the imputed complete data sets for each shift in treatment effect.
3. Combine analysis results into a final result for each shift in treatment effect.

Step 1:

The fully conditional specification (FCS) method will be used to impute missing values for MD-CRS part II total score change values and will use age group at baseline, treatment arm, and baseline MD-CRS part II total score to determine the scores (500 imputations will be created).

The SAS code for the imputation is as follows:

```
%macro midata(data=, smin=, smax=, sinc=, out=);  
data &out; set _null_; run;  
%let ncase=%sysevalf((&smax-&smin)/&sinc, ceil);  
%do jc=0 %to &ncase;  
%let sj=%sysevalf(&smin + &jc*&sinc);  
proc mi data=&data out=outmi seed=724375 nimpute=500;  
class arm agegrp region;  
fcs regpmm;  
mnar adjust (_9 /shift=&sj adjustobs=( arm='TEV-50717'));  
mnar adjust (_12 /shift=&sj adjustobs=( arm='TEV-50717'));  
mnar adjust (_15 /shift=&sj adjustobs=( arm='TEV-50717'));  
  
var arm agegrp region base _9 _12 _15; run;  
data outmi; set outmi; shift=&sj; run;  
data &out; set &out outmi; run;  
  
%end;  
%mend midata;  
  
%midata(data=final, smin=, smax=, sinc=, out=out1);
```

Values should be added for smin, smax, and sinc. Per current definitions, these should be smin=0, smax=2.0 (or estimated treatment effect from primary analysis if it is larger than 2) and sinc=0.2.

Step 2

The resultant complete data sets will be analyzed using the same model as the primary analysis – see [Appendix 1](#) - Step 2. The SAS code is as follows:

```
data all; set out1;
  avisitn=9; chg=_9; output; avisitn=8; chg=_8; output; avisitn=12; chg=_12; output; run;

proc sort data=all; by shift _imputation_ arm avisitn; run;

proc mixed data=all order=data; by shift _imputation_ ;
  class usubjid arm avisitn agegrp region;
model chg=arm avisitn arm*avisitn agegrp region base / ddfm=kr;
  repeated avisitn / type=un subject=usubjid;
  lsmeans arm*avisitn / diff cl;
  ods output diffs=diff(where=(avisitn=_avisitn )) lsmeans=lsm; run;
```

Step 3

The results from the imputed data analysis will be combined using PROC MIANALYZE which will provide the LS mean and standard error of the LS mean for each treatment group at each visit as well as the LS mean difference, 95% CI and resultant p-value between the TEV-50717 and placebo groups at each visit. The SAS code is as follows:

```
proc sort data=diff; by shift avisitn arm; run;
proc sort data=lsm; by shift avisitn arm; run;

proc mianalyze data=diff; by shift avisitn arm;
  modeleffects estimate;
  stderr stderr;
  ods output ParameterEstimates=estdiff; run;

proc mianalyze data=lsm; by shift avisitn arm;
  modeleffects estimate;
  stderr stderr;

ods output ParameterEstimates=estlsm; run;
```

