2.4. Sample Size and Power Considerations

The initial sample size estimation of approximately 185 patients randomized to TEV-50717 versus placebo in a 2:1 ratio (approximately 124 in the TEV-50717 group; approximately 61 in the placebo group) is the sample size required to obtain a statistically significant result in the primary analysis based on a 1-sided test for mean difference at a significance level of $\alpha=0.025$ with a power of approximately 90%, assuming a mean difference of 1.8 and a standard deviation (SD) of 3.5 in each treatment group.

Based on Protocol Amendment 05, the initial planned sample size has been reduced to approximately 65 patients randomized to TEV-50717 versus placebo in a 2:1 ratio (approximately 43 in the TEV-50717 group; approximately 22 in the placebo group).

The initial assumptions regarding the mean difference and SD are based on the change from baseline to month 6 in patients treated with trihexyphenidyl reported by [Battini et al \(2014\)](#), assuming an effect size of 55% for TEV-50717 versus placebo. The effect size of 55% was assumed based on the observed effect sizes of TEV-50717 in the pivotal studies in Huntington's disease and tardive dyskinesia. In the current study, these assumptions correspond to a mean difference of 2.0 in MD-CRS part II total score and an SD of 3.5 in each treatment group.

The rate of missing not at random (MNAR) data for the primary analysis is expected to be 10%. MNAR data will be imputed in a conservative manner as if they were obtained from patients in the placebo treatment group, regardless of the actual treatment group. As a result, the mean difference is expected to be reduced from 2.0 to 1.8 in the primary analysis. The impact of the missing data imputation on the SD is negligible.

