6.2.4.1.1. MNAR Tipping Point Analysis

Details for tipping point analysis are described below:

- a. For patients that completed the study, intermittent missing data are considered as MAR and will be imputed by the predictive mean matching multiple imputation method (Heitjan and Little 1991, Schenker and Taylor 1996). The imputation model will include age group at baseline, region, treatment group and MD-CRS part II total score at baseline, week 9 and week 12.
- b. For patients who discontinued due to any reason, all missing data will be imputed using the same predictive mean matching multiple imputation method. The imputed values will be adjusted under a MNAR assumption:
 - Patients randomized to TEV-50717: the first missing value after patients drop out will be analyzed assuming the treatment effect is worsened by δ (where $\delta_1 = 0$ to 2 or estimated treatment effect based on the primary analysis, whichever is higher, in step of 0.2) compared to the patients who have no missing value. $\delta \geq 0$ will be used as a shift to adjust the imputed values, since higher MD-CRS score corresponds to the more severe movement disorder.
 - Patients treated with placebo: the observed treatment effect for placebo-treated patients will be used for imputing missing value in the placebo population for all shift parameters.

The shift will be applied only for the first visit with missing data and will not be applied for later time points as these values are shifted through the condition on the previous time points. For each δ value, 500 imputed datasets will be obtained.

- c. The resulting complete, imputed datasets will each be analyzed using the same model as the primary analysis model, and the resulting statistics combined using methodology provided by Rubin (1987) and Little and Rubin (2002). Refer to Appendix 1; start at Step 2.

The complete multiple imputation methodology, along with the SAS code, is detailed in Appendix 2.

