7. MULTIPLE COMPARISONS AND MULTIPLICITY

The primary efficacy endpoint will be tested at the 1-sided significance level of $\alpha=0.025$.

If the primary endpoint is statistically significant (p-value ≤ 0.025), the 5 key secondary hypotheses will be tested using a hierarchical approach at the 1-sided significance level of $\alpha=0.025$, in the following order: (1) MD-CRS part I total score, (2) CaGI-I, (3) CGI-I, (4) UHDRS-TMC (centrally-read), and (5) UHDRS-TMD (centrally-read)

No multiplicity control will be applied to the sensitivity analysis or other endpoints.

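### The tipping-point program in SAP Appendix 2 omits week 15, reverses the treatment contrast and applies a different shift rule from Section 6.2.4.1.1

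*SAP*

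**What the plan says.** Section 6.2.4.1.1 imputes completers' intermittent gaps under MAR without a penalty. For TEV-50717 patients who discontinued, it worsens the imputed value by delta: "The shift will be applied only for the first visit with missing data and will not be applied for later time points". It then applies the primary analysis model and names Appendix 2 as the complete methodology with code.

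Appendix 2, Step 1 imputes `_9`, `_12` and `_15`. It carries one adjustment statement for each visit, the last being "mnar adjust (_15 /shift=&sj adjustobs=( arm='TEV-50717". The only condition is the arm.

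Appendix 2, Step 2 creates the analysis records with "avisitn=9; chg=_9; output; avisitn=8; chg=_8; output; avisitn=12; chg=_12; output; run", sorts them with "proc sort data=all; by shift _imputation_ arm avisitn; run", and runs the mixed model under `order=data`. The matching step in Appendix 1 outputs weeks 9, 12 and 15 and sorts by descending arm.

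On the range, Appendix 2 says "Delta will be in the range of 0 to 2". The same sentence raises the upper end to the estimated treatment effect when that exceeds 2, as does Section 6.2.4.1.1. The step is 0.2.

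Section 6.2.4.1.2 takes the MAR sensitivity analysis from the delta = 0 run. Section 6.3.1.2 carries the same sensitivity analyses to the key secondary endpoints.

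**The concern.** The tipping-point analysis is meant to show how bad outcomes after dropout must be before the week-15 conclusion fails. A program that produces no week-15 record cannot show this. A reversed contrast invites misreading of the estimate and its interval. Two different shift rules, one in the text and one in the code, leave open which penalty was pre-specified, and the choice could be made after unblinding. If delta also stops before significance is lost, the analysis yields no tipping point to report.

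**Working it through.** **Visits.** Step 1 imputes `_9`, `_12`, `_15`. Step 2 outputs 9, 8, 12. `_8` is not among the imputed variables and `_15` is never output, so only weeks 9 and 12 can be estimated. The delta = 0 run has the same gap.

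**Contrast.** With arm labels PLACEBO and TEV-50717, the ascending sort under `order=data` makes placebo the first level, so the difference is placebo minus TEV-50717. Appendix 1 gives TEV-50717 minus placebo. The estimate and confidence limits change sign; a two-sided p-value does not change.

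**Shift rule.** Take a patient first missing at week 12. This is the relevant case: the mITT set requires a post-baseline central reading, and Table 2 assigns early-termination MD-CRS data from days 2 to 73 to week 9. Let b be the slope of week 15 on week 12 in the imputation model. The SAP does not give b, so it is an assumption.

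- Text: week-15 shift = b × delta
- Code: week-15 shift = (1 + b) × delta

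| b | Text, delta = 2 | Code, delta = 2 | Ratio |
|---|---|---|---|
| 0.4 | 0.8 | 2.8 | 3.5 |
| 0.7 | 1.4 | 3.4 | 2.4 |
| 0.9 | 1.8 | 3.8 | 2.1 |

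The ratio depends on b, but the absolute gap is always delta. This is linear propagation. The code uses predictive mean matching within fully conditional specification, and its exact shift was not verified in SAS.

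**The plan's own figure.** Section 2.4 gives about 185 patients (124/61), "based on a 1-sided test for mean difference at a significance level of" 0.025, "with a power of approximately 90" per cent, for difference 1.8 and SD 3.5. Placebo n = 1.5 × (1.960 + 1.282)² × (3.5/1.8)² ≈ 60, so 180 in total. Power at 124/61 is 90.8%. The figure reproduces to within 3%.

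**Range at the current size (43/22).** SE = 3.5 × √(1/43 + 1/22) = 0.917. Section 7 sets the threshold: "If the primary endpoint is statistically significant (p-value ≤ 0.025", one-sided. The observed benefit d must therefore reach about 1.96 × 0.917 = 1.80.

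Movement in z at delta = 2 is (missing share in the TEV-50717 arm) × (week-15 shift) / 0.917. With b = 0.7:

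| Missing | Text | Code |
|---|---|---|
| 10% | 0.15 | 0.37 |
| 20% | 0.31 | 0.74 |
| 30% | 0.46 | 1.11 |

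At 10% missing, even if delta carried fully to week 15, the delta needed to tip is (d − 1.80)/0.10. That is about 2.0 for d = 2.0, 7.0 for d = 2.5 and 12.0 for d = 3.0, while the range ends at 2.0, 2.5 and 3.0. Only observed differences from about 1.80 to 2.00 tip.

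A small simulation used 43/22 patients, SD 3.5, true difference 2.0, between-visit correlation 0.7, dropout spread evenly over visits, regression imputation, a week-15 mean comparison and 400 trials per setting. The share of significant results that tip by the end of the range was:

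| Missing | Text rule | Coded rule |
|---|---|---|
| 10% | 7% | 22% |
| 20% | 28% | 66% |
| 30% | 46% | 97% |

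These shares are indicative only.

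**The case against.** The intended visits are clear: Section 6.2.4.1.1 and Appendix 2 both call for the primary model and point to Appendix 1, Step 2, which outputs 9, 12 and 15. A programmer would find the missing week-15 row at once, so a wrong week-15 result could not pass unnoticed. The sign reversal would also be visible. These points stand, but they do not settle the shift rule, where text and code each describe a runnable analysis and give different answers.

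A reader might infer that a one-sided p-value necessarily falls in the wrong tail. Appendix 2 shows no one-sided step, so this follows only if that value is derived as for the primary analysis.

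A bounded delta grid is also not an error in itself. Its floor of 2 equals the full assumed effect of 2.0 in Section 2.4, and surviving that penalty is informative. The 10% is the plan's MNAR rate, whereas the shift covers all discontinuations, so the relevant share may be higher. The range is therefore a secondary point.

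**Conclusion.** Wrong as written. Appendix 2 cannot deliver the week-15 tipping-point analysis or the MAR analysis taken from it. It also reverses the contrast and uses a shift rule that contradicts Section 6.2.4.1.1. At delta = 2 and an assumed slope of 0.7, a patient first missing at week 12 is moved 1.4 points by the text and 3.4 by the code.

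Under the text rule, with SE about 0.92 and about 10% missing, the range ends before significance is lost for most significant results. This weakens at 20–30% missing and under the coded rule.

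Three stronger readings are not supported:

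- That the analysis would report robustness almost regardless of the data. At 20–30% missing the text rule tips 28–46% of significant results in the simulation, and the coded rule tips 66–97%.
- That the two rules differ 4.5-fold. That needs a patient missing from week 9, which is rare in the mITT set, and one particular slope model (0.98 against 4.38 points).
- That this is the only stress test of missing data. The primary analysis already uses jump-to-reference for MNAR cases, and Section 6.2.4.3 adds a week-15 ANCOVA without multiple imputation.

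Sensitivity analyses lie outside the multiplicity scheme in Section 7, so the primary inference is not affected.

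**What to change.** - In Appendix 2, Step 2, output weeks 9, 12 and 15, and sort by descending arm as in Appendix 1.
- Impute completers' intermittent gaps under MAR first, without a shift.
- State one shift rule, identical in Section 6.2.4.1.1 and the code and limited to TEV-50717 patients who discontinued. Say how much of delta is meant to remain at week 15.
- Continue delta in steps of 0.2 until the one-sided p-value exceeds 0.025, and report that delta.
- State the direction of the difference and how the one-sided p-value is obtained.

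The cost is a short correction to SAP text and code plus further computing runs. No new data are needed and the primary analysis does not change.
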